## 5.2 Handling of study interventions

- 5.2.1 **PCP clinic instruction:** As part of the QI initiative, all PCP clinic sites will receive instruction on how to identify and collect patient-reported outcomes for patients with back pain. QI staff will work with physician champions at each practice site and their staff to ensure smooth processes for administering the screening tools. They will also receive an educational presentation, including a primer on guidelines for LBP, an overview of the Chronic LBP Questionnaire, the STarT Back Tool, and the Oswestry. Sites included in the GBC arm will not be instructed to alter their normal clinical procedures beyond data collection while those in the intervention arm will be coached by QI staff on referral to PIPT.
- 5.2.2 **PIPT physical therapist education:** To educate physical therapists in the referral areas for the intervention arm, a PT continuing education program will be provided for physical therapists that includes PT guidelines, principles of PIPT, clinical application, and adherence. Initial training of physical therapists will consist of a 1-day (8-hour) course that offers:
- 1) A condensed and focused summary of the principles of pain neuroscience and cognitive behavioral therapy (CBT),
  - 2) Case examples of using PIPT principles with back pain patients,
  - 3) Basic training in specific communication skills and styles that can enhance patient motivation for attitudinal and behavioral change, and
  - 4) Interactive, experiential training in delivering brief educational and PIPT approaches.

Ongoing training to promote adherence to the PIPT skills in clinical treatment will be provided through telephone and email access to trainers/mentors, online

discussion groups, and an adherence checklist for use during treatment of high risk patients. The intervention is designed to be a practical, patient-centered, and activity-based treatment, and will utilize American Physical Therapy Association (APTA) Orthopaedic Section Clinical Practice Guidelines.

### **5.3 Concomitant interventions**

In keeping with the pragmatic nature of the trial, there will be no restrictions on patients taking part in other clinical trials.

### **5.4 Adherence assessment**

5.4.1 **Patient adherence:** Patients will be compensated for their participation in data collection: one payment of \$15 will be mailed after the completion of the 6-month assessment. All care will be paid for through existing health insurance benefit structures, established programs for underserved patients, or will be self-pay.

5.4.2 **Provider adherence:** Approaches will be implemented to enhance provider adherence within the context of the EMR. PCP stakeholders strongly believed that time restrictions would not permit them to enter into the EMR the data necessary to identify baseline characteristics (2-item chronic questionnaire, STarT Back Tool, and Oswestry LBP Questionnaire). As a result, the portal or tablet-based approaches programmed within the EMR environment would be the first line of data collection utilized uniformly throughout the study sites. Portal and tablet-based approaches are becoming increasingly implemented in PCP environments, supporting generalizability. The study team will not dictate treatment fidelity approaches for PT provider adherence, but will implement a “checklist” that includes reference guidelines for the PIPT approach. This checklist will be included in the routine communication that occurs between the physical therapist and a referring PCP.

## 6 Study procedures

### 6.1 Schedule of evaluations

**Table 2: Schedule of evaluations**

| Assessment                    | Screening and Enrollment | 6-Months | 12-Months |
|-------------------------------|--------------------------|----------|-----------|
| Chronic LBP Questionnaire     | ✓                        | ✓        |           |
| STarT Back Tool               | ✓                        |          |           |
| Oswestry LBP Disability Index | ✓                        | ✓        |           |
| EMR Medical Resource Use*     |                          |          | ✓         |

*\*EMR data for UPMC, BMC, JHM, IH*

A detailed flow diagram for each regional site is provided in Appendix 5.

### 6.2 Description of evaluations

- 6.2.1 **Screening evaluation:** Patients receiving care for acute back pain will be given the three-part assessment during the PCP visit scheduling process (up to seven days prior) or upon arrival at the clinical site. Candidates will be deemed eligible for the study if they are identified as an acute LBP patient. Those in the high risk STarT Back group will be identified for enrollment in the RCT for the primary and secondary outcomes, and those in the low or medium risk STarT Back groups will be identified for enrollment in the observational cohort for secondary outcomes. The screening evaluations are part of normal practice, and results for all screened patients will be available for clinical staff to use in the EMR.
- 6.2.2 **Consent process:** The University of Pittsburgh Institutional Review Board (IRB) has approved a waiver of informed consent/HIPAA authorization to access, record, and use protected patient health information/patient medical record information for review and analysis of medical record data for the conduct of this study at UPMC clinics and Intermountain Healthcare clinics. It has also approved a waiver for the requirement to obtain a written informed consent for completion of questionnaires and interviews at those sites. Verbal consent will be obtained by telephone or electronic consent by email prior to the 6-month assessment by research staff from the University of Pittsburgh. A letter will be mailed from the Healthsystem prior to the contact by research personnel to inform the patients about the research study and provide them an option of opting out of receiving any additional follow up by calling a project office telephone number or sending an email message to the project email address. Participants will be given the option of completing the 6-month assessment as a hard copy self-report, which will be mailed to the project office with a consent template with their name recorded for tracking. The research involves no more than minimal risk to the participant, the waivers will not

adversely affect the rights and welfare of the participant, and the research could not practicably be carried out without the waivers.

Specifically,

- The study is comparing two standard-of-care treatments that patients could receive regardless of participation in the study,
- These standard clinical approaches do not require consent outside of the research context,
- A total sample size of at least 8,760 participants is needed from these sites to meet the aims of the study,
- The study needs to be conducted within the clinical setting (i.e., a pragmatic trial), which typically allows <15 minutes per patient visit; the consent/authorization procedures would disrupt the clinical setting and potentially impact patient care.

6.2.3 **Enrollment and baseline evaluation:** Upon determination of eligibility, patients will be enrolled in the QI initiative of the study. Baseline data will be contained in the EMR and extracted for study purposes, including screening results, demographic information, billing information, and clinical data (e.g., diagnoses, referrals to specialists). Patients identified as high risk, acute LBP patients in the intervention arm will be referred to PIPT, and this referral will also be captured in the EMR. The list of baseline variables to be extracted from the EMR is provided in Appendix 6.

6.2.4 **Randomization:** As a cluster RCT, randomization will occur at the clinic level and not the patient level; therefore, randomization is not a factor in the enrollment or baseline evaluation.

6.2.5 **Follow-up:** Follow-up to the initial screening and QI enrollment visit will occur through three mechanisms:

- 1) **Referral to PIPT:** For eligible patients referred to PIPT, follow up at PT will be evaluated through the checklist completed at the PT visit and returned to the PCP site. This checklist will indicate use of the PIPT approach and number of PT sessions.
- 2) **Six-month assessment:** Research staff will contact all enrolled patients 6 months after their initial visit at all sites and conduct the Chronic LBP Questionnaire and the Oswestry to assess the primary outcomes.
- 3) **Medical resource utilization:** Researchers will also extract data from the EMR at select sites to determine the secondary outcome of LBP-related medical resource utilization of tests, procedures, and pharmaceuticals by enrolled patients for 12 months after the initial visit.

The list of variables for medical resource utilization is provided in Appendix 6.

## 7 Safety assessments

All clinical activities related to this trial will be performed in accordance with normal clinical practice. Safety concerns and adverse events arising from clinical operations within the PCP or PT settings will also follow normal clinical procedures. Adverse events related to the research study would be limited to a data breach of confidentiality. This would not require patient report but would require study report, following Office of Information Security protocols at the University of Pittsburgh for reporting and resolution.

## 8 Intervention discontinuation

Enrollees who do not follow the clinical practices contemplated within this trial or do not respond to the follow-up calls will be documented but not discontinued.

## 9 Statistical considerations

### 9.1 General design issues

- 9.1.1 **A primary aim (PA1)** is to determine in patients with acute LBP who are deemed high risk for transition to chronic, what is the proportion of patients transitioning to chronic LBP by the time of the 6-month assessment who are treated with 1) GBC compared to 2) GBC+PIPT.
- 9.1.2 **H1:** GBC+PIPT will be more effective than GBC alone for preventing patients with high risk acute LBP from transitioning to chronic LBP.
- 9.1.3 The primary outcome will be determined by patients' responses to the Chronic LBP Questionnaire at 6 months. The proportion of patients that have transitioned will be compared across the two study arms.
- 9.1.4 **PA2** is to compare patient-centered outcomes of LBP-related function (e.g., lifting, walking, sleeping) for high risk patients between the two study arms at the 6-month assessment.
- 9.1.5 **H2:** GBC+PIPT will be more effective than GBC alone for improving functional outcomes for patients with high risk acute LBP.
- 9.1.6 This primary outcome will be measured using patients' responses to the Oswestry LBP Questionnaire at baseline versus at 6 months to determine changes in the score.
- 9.1.7 **SA3** is to compare acute LBP-related medical resource utilization (e.g., imaging, epidural steroid injections, opioids) for high risk patients between the two study arms.

- 9.1.8 **H3:** GBC+PIPT will be more effective than GBC alone for reducing LBP-related medical resource utilization for patients with high risk acute LBP.
- 9.1.9 This secondary outcome will be measured by retrieving patient medical resource utilization data from the EMR for LBP-related tests, procedures, specialty visits, and pharmaceuticals for 12 months after the initial visit.
- 9.1.10 **SA4** is related to PA1-2 and SA3 but will determine the proportion of medium and low risk patients that transitions to chronic LBP; patient-centered outcomes (e.g., functional impact); and LBP-related medical resource utilization.
- 9.1.11 Outcomes for this aim will utilize the same measures and sources as PA1-2 and SA3 for the medium and low risk patients.
- 9.1.12 **SA5** is to conduct subgroup analyses for PA1-2 and SA3 on patients with lower socioeconomic status (using insurance as a proxy) and the co-morbid conditions of smoking, depression, and obesity.
- 9.1.13 **H5:** GBC+PIPT will have less transition to chronic LBP and will be more effective than GBC alone for improving functional outcomes and reducing LBP-related medical resource utilization for the subgroup of patients who are underserved or with depression. Because the interventions being studied do not specifically target obesity and smoking, and the relationship of these variables to transition to chronic are unclear, group x obesity interactions are not expected.
- 9.1.14 Outcomes for this aim will utilize the same measures and sources as PA1-2, SA3 but will also include EMR data on patient co-morbidities, smoking status, and socioeconomic status.
- 9.1.15 **Missing data:** Baseline characteristics, such as age, gender, and health insurance status, will be compared between patients with complete assessment data to those with missing data by treatment group in order to assess potential biases that may exist in the complete case analysis. Sensitivity analyses for the primary and secondary outcomes will be conducted using several methods, which have different missing data assumptions.
- 1) Complete case analyses, which assumes missing data are completely at random,
  - 2) Multiple imputation using M=10 imputations, which assumes missing at random, and
  - 3) Assigning poor scores and good scores for missing values differentially by treatment group, which aligns with non-ignorable missingness (the data missingness is nonrandom and related to the actual value).

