## 9.4 Outcomes

- 9.4.1 **Primary outcome 1:** To test the effect of the intervention on preventing the transition from acute to chronic LBP (**PA1**), the study team will compare the rates of transition to chronic LBP at 6 months, based on the results of the 6 month Chronic LBP Questionnaire, between enrolled patients at intervention clinics and enrolled patients at comparator clinics. This comparison will be conducted for high risk patients at 6 months (**PA1**) as well as low and medium risk patients (**SA4**) and specific subgroups (**SA5**).
- 9.4.2 **Primary outcome 2:** To test the effect of the intervention on improving patient-centered outcomes of back-related function (**PA2**), the study team will compare changes in the Oswestry scores from baseline to 6-month assessment between enrolled patients at intervention clinics and enrolled patients at comparator clinics. This comparison will be conducted for high risk patients at 6 months (**PA2**) as well as low and medium risk patients (**SA4**) and specific subgroups (**SA5**).
- 9.4.3 **Secondary outcomes:** To test the effects of the intervention on reducing medical resource utilization (**SA3**) the study team will compare LBP-related medical resource utilization data for enrolled patients at intervention clinics and enrolled patients at comparator clinics for a period of 12 months. This comparison will be conducted for high risk patients (**SA3**) as well as low and medium risk patients (**SA4**) and specific subgroups (**SA5**). The medical resource utilization data will be identified and categorized using Healthcare Common Procedure Coding System (HCPCS) Level 1 (CPT-4) and 2, and ICD-10 codes. These data will be used to evaluate the frequency, intensity and composition of services received within the participating PCP/PT practices as well as care delivered in other community practices and facilities. The study team will investigate evaluation & management services (PCP & specialist), diagnostic testing, rehabilitation services, and medical procedures. Furthermore, the study team will also capture prescribing patterns for key drug classes commonly used for LBP management such as non-steroidal anti-inflammatory drugs (NSAIDs), acetaminophen (Tylenol), opioid analgesics, skeletal muscle relaxants, antidepressants (e.g., tricyclic antidepressants and duloxetine), and drugs for neuropathic pain (e.g., gabapentin).

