- 9.5.3 **Secondary outcome:** Analyses of health care utilization data (**SA3**) will use generalized linear mixed models with the distribution determined by the type of data but still controlling for the cluster randomized trial design by having random effects for clinics. Logit link (binary distribution) will be used for health care outcomes, such as surgery, that are dichotomous (Yes/No) variables. For outcomes resulting in count data over the time frame such as number of outpatient visits for back pain, hospitalizations or ER visits, Poisson or negative binomial distribution with log link will be used to compare the event rates controlling for the period of follow up. The secondary aims (**SA4** and **SA5**) would use a similar approach.

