### Definition and questionnaire rules:

- “Chronic” = greater than 3 months (Q1c) + at least half the days (Q2b)
- “Acute” = all else Q1a, Q1b, or Q1c+Q2a
- If patient answers 1a or 1b, stop and patient is acute
- If patient answers 1c, proceed to question 2
- If patient answers 2a, patient is acute
- If patient answers 2b, patient is chronic

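### The SA3/H3 utilization models do not adjust for each patient's use before the initial visit, which gives away precision and leaves chance differences between clinics uncorrected

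*Combined protocol and SAP*

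**What the plan says.** **Outcome window.** Section 9.1.9 defines the SA3 outcome as "retrieving patient medical resource utilization data from the EMR for LBP-related tests, procedures, specialty visits, and pharmaceuticals for 12 months after the initial visit". Section 6.2.5 gives the same window: "utilization of tests, procedures, and pharmaceuticals by enrolled patients for 12 months after the initial visit". Section 9.4.3 compares use between "enrolled patients at intervention clinics and enrolled patients at comparator clinics for a period of 12 months", so the contrast is of post-visit levels and not of change.

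**Model.** Section 9.5.3 uses generalized linear mixed models with random clinic effects and a logit link for yes/no outcomes. For counts, "Poisson or negative binomial distribution with log link will be used to compare the event rates controlling for the period of follow up". It names no covariate for earlier use.

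**Drugs.** Section 9.4.3 says the team will "capture prescribing patterns for key drug classes commonly used for LBP management", and lists opioids, antidepressants and neuropathic pain drugs among others. Neither that section nor the medication list in Appendix 6 says how indication is decided or how new prescriptions are told apart from continuing ones.

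**Contrast.** Section 9.5.2 (PA2) controls for baseline Oswestry.

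**Text that comes near the point:**
- Section 6.2.3 extracts baseline billing and clinical data, including specialist referrals. It gives no look-back window and no role for these data in SA3.
- Appendix 6 lists demographics, body mass index, tobacco use, comorbidity and insurance as baseline variables. Its encounter and medication lists carry no time window.
- Section 9.2.5 adjusts for observed baseline differences between arms, but only in sensitivity analyses and without naming prior use.

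**The concern.** H3 is a formal hypothesis about reducing LBP-related use. A patient's earlier use can be expected to predict later use, and the four regions that supply utilization data (Section 10.1.3) could supply it from the same records. Leaving it out of the model leaves explainable variation in the comparison.

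The entry rules allow earlier treatment. Section 4.2 excludes only red flags. Appendix 1 defines acute as "all else Q1a, Q1b, or Q1c+Q2a", so it includes pain of more than three months if it interferes on less than half the days. Section 2.3.3 describes high risk patients as having comorbid depression and anxiety, so some may already take a drug in a counted class.

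Section 3.2 balances clinics on back pain volume and on Medicaid/self-pay share, not on prescribing or referral habits. With whole clinics randomized, chance differences in those habits can be material. The documents give no power, effect size or intraclass correlation for H3, so nothing shows how much precision SA3 can spare.

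**Working it through.** The plan states no figure for H3, so there is none to reproduce. The size of the point can only be bracketed.

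**Inputs from the plan**
- Regions with utilization data: four of five (Section 10.1.3). At the minimum of 12 clinics per region (Section 3.2), 4 × 12 = 48 clinics, or 24 per arm.
- Enrolled high risk patients per clinic: 31 on average (Section 9.2.2).
- Intraclass correlation (ICC): 0.05 (Section 9.2.3). The plan gives this for PA1; using it for utilization is an assumption.

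**Inputs assumed**
- Correlation r between an outcome's pre-visit and post-visit values: 0.3 to 0.6.
- A linear model and equal clinic sizes.

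**Step 1: upper end, same r within and between clinics.** The variance left after adjustment is 1 − r², and the effective sample is multiplied by 1/(1 − r²).

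**Step 2: lower end, only within-clinic variation explained.** The variance of a clinic mean is proportional to ICC + (1 − ICC)/31 = 0.05 + 0.95/31 = 0.05 + 0.0306 = 0.0806. The between-clinic share is 0.05/0.0806 = 62%, and adjustment does not touch it. After adjustment the variance is 0.05 + 0.0306 × (1 − r²), and the gain is 0.0806 divided by that.

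| r | 1 − r² | Gain, same r at clinic level | Variance, within-clinic only | Gain, within-clinic only |
|---|---|---|---|---|
| 0.3 | 0.91 | 10% | 0.0779 | 4% |
| 0.5 | 0.75 | 33% | 0.0730 | 10% |
| 0.6 | 0.64 | 56% | 0.0696 | 16% |

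**Step 3: chance imbalance.** Take an any-use outcome. Assume that 25% of patients without prior use become users, and that every prior user counts as a user afterwards. If the arms differ by 5 points in the share of prior users, any-use differs by 0.05 × (1 − 0.25) = 3.75 points with no treatment effect. Both assumed figures are illustrative.

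**Step 4: what the existing text supplies.** The Section 9.2.5 safeguard acts only on a difference that has been seen, and prior use cannot be compared between arms unless it is extracted. Adjustment also gains precision when the arms are balanced, which a sensitivity analysis triggered by imbalance does not provide.

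**The case against.** **The outcome is already restricted.** Sections 1.2.1, 3.3.3, 6.2.5, 9.1.9 and 9.4.3 tie it to LBP, and Section 9.4.3 identifies use by procedure and ICD-10 codes. This stands. It should limit carry-over for imaging, injections and surgery. A reader might infer that a long-standing antidepressant for depression will count as LBP use. The documents do not say so; they give no rule either way. The gap is therefore clearest for drug classes.

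**Some earlier care is captured.** Section 6.2.3 extracts billing data and referrals at baseline, so it would be wrong to say that the plan ignores everything before the visit. What is missing is a look-back window, prior medication and any use of such data in the SA3 model.

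**Randomization and the random clinic effect cover it.** In expectation they do, and chance differences between clinics are part of what the standard error represents. A reader might infer that the H3 estimate is biased; the design does not support that. What remains is that the standard error is larger than it need be.

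**New use should then be the test of H3.** This is also tempting. Suppose 20% of patients are prior users who count as users in both arms, and new use is 25% against 15%. The any-use rates are 0.20 + 0.80 × 0.25 = 0.40 and 0.20 + 0.80 × 0.15 = 0.32, so the risk ratio moves from 0.60 to 0.80. With 24 clinics per arm, 31 patients each, ICC 0.05 and a cluster-size coefficient of variation of 0.65, the design effect is 1 + ((1 + 0.65²) × 31 − 1) × 0.05 = 3.15. The effective sample is 24 × 31/3.15 = 236 per arm. Power at an assumed two-sided 5% level falls from 78% to 44%. But the 20% has no source, and the calculation assumes that the intervention cannot change continuing use. Reducing or stopping continuing use is a legitimate effect under H3, and Section 2.3 names less exposure to drugs such as opioids as an aim. A new-use outcome would discard it.

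**Conclusion.** The concern holds as a matter of precision. No look-back period or prior-use covariate appears anywhere in the plan for SA3, and Sections 6.2.3 and 9.2.5 do not supply one. The benefit of adding it runs from a few percent of effective sample to more than half, depending on r and on whether prior use also explains differences between clinics. The logit, Poisson and negative binomial models of Section 9.5.3 will not follow the linear approximation exactly. The documents do not support a claim of systematic bias, any estimate of how many patients enter already on treatment, or a change in what H3 tests. This concerns a secondary outcome; its strength is that the remedy is cheap and uses records the study already queries.

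**What to change.** 1. In Section 9.1.9 and Appendix 6, extract the same utilization variables for a fixed period before the initial visit, for example 12 months, at the four EMR regions. State the window for each Appendix 6 list.
2. In Section 9.5.3, include each outcome's pre-visit value as a prespecified covariate in its SA3 model, with an indicator for patients who have no look-back.
3. Keep all LBP-related use as the H3 outcome. Report new use among patients with no prior use of each drug class as a supporting analysis.
4. State how a prescription in a listed class is judged LBP-related, or that no such judgment is made.

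**Cost.** The EMR query needs an earlier start date and the analysis plan a few added sentences. Someone must check that the waivers described in Sections 6.2.2 and 11.1 cover the look-back, including with the separate IRBs for Boston and Baltimore. No patient contact or clinical procedure changes. The main weakness is incomplete history for patients new to a health system. The indicator handles this in the model, but such patients could be misclassified as new users in the supporting analysis, so their number should be reported.

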## 9.2 Randomization, sample size and power – RCT cohort

- 9.2.1 **Randomization** will occur at the clinic level, which was chosen for the pragmatic reason that randomizing patients within a clinic would result in cross contamination of the interventions within the same clinic. The biostatisticians and the individuals conducting the 6-month assessments will be blinded to the randomization assignment to avoid bias in analyses and data capture.
- 9.2.2 **Sample size** is based on the first primary outcome of the transition rate to chronic LBP at month 6. We propose to enroll N=1860 high risk acute LBP patients. We are targeting an average of n=31 enrolled high risk patients per clinic ( $60 \times 31 = 1860$ ) to account for the variation in cluster sizes (assuming coefficient of variation=0.65) and 40% non-response rate at 6 months.
- 9.2.3 **Power:** With a total of 60 PCP clinics for randomization, m=30 clinics per intervention strategy and fixed n=10-14 completers per clinic for the 6-month assessment, we will have just over 80% power to detect a 40% reduction in transition to chronic LBP assuming the control arm has a transition rate of 25%-30% and the intraclass correlation is 0.05, which is an upper bound for what has been observed in other cluster randomized trials with respect to either pain or LBP. Assuming that low and medium risk subjects with acute LBP have an expected 20% transition to chronic and using data on obesity and smoking rates based on national surveys, depression rates based on prevalence rates reported in primary care, and proportions of underserved patients estimated from patient registries at each of the five regional sites, the planned sample size for the observational cohort is sufficient to detect at least a 30% relative difference (6% absolute difference) from 20% with powers ranging from 79% to 87%. The study would have 65% power to detect a 40% relative or 8% absolute difference (hypothesized increased rate of transition) for the depression subgroup.

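### Ten imputations with 40% planned non-response leave the multiple-imputation p-value dependent on the random seed when the result is near 0.05; a larger M costs only computing time.

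*Combined protocol and SAP*

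**What the plan says.** Section 9.1.15 (Missing data) states that "Sensitivity analyses for the primary and secondary outcomes will be conducted using several methods". It lists three: complete cases, "Multiple imputation using M=10 imputations, which assumes missing at random", and differential assignment of good and poor scores by arm. No reason is given for ten. The section states no seed, imputation model or check of Monte Carlo error.

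Section 9.2.2 says "We propose to enroll N=1860 high risk acute LBP patients", "targeting an average of n=31 enrolled high risk patients per clinic", and allows for unequal clinic sizes ("assuming coefficient of variation=0.65") and a "40% non-response rate at 6 months". About 0.40 × 1860 = 744 six-month outcomes would therefore be imputed in the RCT cohort. Section 9.2.3 sets the ICC at 0.05, described as an upper bound.

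**The concern.** Multiple imputation draws random values, so two analysts who follow the same plan with different seeds get different answers. The size of that difference depends on M and on how much information is missing. Ten imputations give nearly full statistical efficiency, but efficiency describes average precision. It does not say whether one reported p-value or interval would come out the same on a second run.

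By the plan's own labelling, multiple imputation is the only one of the three methods that rests on missing at random, and it brings the non-responders back into the comparison. The trial is powered only slightly above 80%, so a result near the line is plausible. In that case the reported agreement or disagreement between the imputed and primary analyses could turn on the seed.

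**Working it through.** **1. The plan's power figure.** Section 9.2.3 gives "m=30 clinics per intervention strategy and fixed n=10-14 completers per clinic for the 6-month assessment" and "just over 80% power to detect a 40% reduction in transition to chronic LBP". With effective n per arm = 30n / [1 + (n − 1) × 0.05], two-sided 0.05:

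- control 25% vs 15%, n = 14: 420/1.65 = 254.5 per arm, power 80.7%;
- control 30% vs 18%, n = 10: 300/1.45 = 206.9 per arm, power 81.8%.

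The stated figure reproduces. The documents give a two-sided 0.05 level only for Table 3 (section 9.3.3), so its use for the RCT is an assumption, though one consistent with this power.

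**2. Fraction of missing information (FMI).** Clinics enrol 31 on average and 31 × 0.60 = 18.6 complete. Within a clinic the patients are correlated, so losing 40% of them loses less than 40% of the information:

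FMI = 1 − [(1 + 30 × ICC)/31] / [(1 + 17.6 × ICC)/18.6]

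- ICC 0.05: 1 − 0.0806/0.1011 = 0.20
- ICC 0.01: 1 − 0.0419/0.0632 = 0.34
- ICC 0: 1 − 18.6/31 = 0.40

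This takes equal clinic sizes and no auxiliary variables. Putting the coefficient of variation of 0.65 into the design effect, 1 + [(1 + 0.65²) × mean size − 1] × ICC, gives 0.17 at ICC 0.05 and 0.32 at ICC 0.01, which changes little.

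**3. Monte Carlo error.** With between-imputation variance B = FMI × T/(1 + 1/M), where T is the total variance, the Monte Carlo SE as a share of the reported SE is √(B/M)/√T = √[FMI/(M + 1)]. For a limiting (infinite-M) p of 0.05, the range over seeds is z = 1.96 ± 1.96 × that ratio:

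| FMI | M | Monte Carlo SE / SE | range of p |
|---|---|---|---|
| 0.20 | 10 | 0.135 | 0.026–0.090 |
| 0.20 | 50 | 0.063 | 0.037–0.066 |
| 0.20 | 100 | 0.044 | 0.041–0.061 |
| 0.40 | 10 | 0.191 | 0.020–0.113 |
| 0.40 | 50 | 0.089 | 0.033–0.074 |
| 0.40 | 100 | 0.063 | 0.037–0.066 |

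Relative efficiency at M = 10, 1/(1 + FMI/M), is 0.98 and 0.96 for the two fractions.

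**4. Check by simulation.** The table counts only noise in the point estimate. Adding noise in the estimated between-imputation variance, and small-sample degrees of freedom (58 for complete data, from 60 clinics), widens the M = 10 ranges to 0.024–0.107 (FMI 0.2) and 0.014–0.156 (FMI 0.4). The same simulation shows where the seed matters at M = 10:

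- limiting p of 0.01: crosses 0.05 for under 1% of seeds (FMI 0.2) or 4% (FMI 0.4);
- limiting p of 0.03: crosses for 15% or 31%;
- limiting p of 0.06: crosses for 27% or 31%.

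Over all trials at the design effect, two seeds disagree on p < 0.05 in 6.2% (FMI 0.2) to 11.5% (FMI 0.4) at M = 10, against 1.9% to 3.0% at M = 100.

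A simulated cluster trial (60 clinics, mean size 31, coefficient of variation 0.65, ICC 0.05, 40% missing at random, beta-binomial imputation, weighted cluster-level logit analysis standing in for the mixed model) gave an FMI of about 0.21. Among data sets with a limiting p of 0.03 to 0.08 (21 to 43 of 250 per scenario), two seeds disagreed 39–41% of the time at M = 10 and 11–17% at M = 100.

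**The case against.** The strongest reply is that this is one of three sensitivity analyses. The primary result comes from the mixed model in section 9.5.1, and nothing in the plan gives the imputed analysis a pass/fail threshold. A sensitivity analysis is read by comparing estimates and intervals, and a shift of 0.135 to 0.19 of a standard error seldom changes that reading. A result that close to 0.05 is equivocal under any seed, and M = 100 still leaves a range. All of this stands, and it keeps the point modest. It does not justify M = 10, since the noise is avoidable.

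Three stronger readings are tempting and are not supported:

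- **That 40% missing outcomes means 40% missing information.** With clustering this holds only at an ICC of zero. At the planning ICC the figure is about 0.20, and auxiliary variables could lower it further.
- **That ten imputations cost many degrees of freedom.** The large-sample formula (M − 1)/FMI² gives 56 at M = 10 and 306 at M = 50 for FMI 0.4, but it ignores that there are only 60 clinics. With the small-sample correction the figures are about 21 and 30 (critical t 2.08 and 2.04). At FMI 0.2 they are 37 and 43 (2.03 and 2.02).
- **That the imputed analysis can neither confirm nor challenge the primary result.** Away from the line it can: a limiting p of 0.01 rarely crosses.

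The 40% is questionnaire non-response. It does not carry over to resource utilization, which is extracted from the EMR.

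**Conclusion.** The concern holds as a point about reproducibility. At M = 10 the seed alone can move a p-value that would settle at 0.05 across about 0.026–0.090 (FMI 0.2) to 0.020–0.113 (FMI 0.4). At M = 100 the corresponding ranges are about 0.041–0.061 and 0.037–0.066. The reading of the analysis is affected only when p is roughly 0.02 to 0.10. The primary conclusion is not at stake.

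The sizes rest on the plan's 40% non-response, 31 enrolled per clinic and an ICC between 0 and 0.05, on no auxiliary variables, and on an assumed two-sided 0.05 level for the RCT.

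**What to change.** In section 9.1.15, replace M = 10 with at least M = 50, preferably 100. State the seed in advance, and report the Monte Carlo error of the imputed estimate and of its p-value. The cost is computing time. Two-seed disagreement falls to between a quarter and a third of its M = 10 level at M = 100 (1.9/6.2 = 0.31; 3.0/11.5 = 0.26), though no finite M removes it entirely.

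Whether the imputation model should carry the clinic effect is a separate question about a model that the plan does not specify. The choice of M does not settle it.
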